5.4.7. COVID-19 Vaccination Guidelines

Administration of a coronavirus disease 2019 (COVID-19) vaccine is not considered contraindicated with idelalisib. Investigators should use their clinical judgment in determining if and when to enroll study participants who have received a COVID-19 vaccine, or whether to continue, interrupt, or discontinue study treatment in subjects who are administered a COVID-19 vaccine during study conduct.

5.5. Accountability for Idelalisib

The investigator is responsible for ensuring adequate accountability of all used and unused study drug. This includes acknowledgement of receipt of each shipment of study drug (quantity and condition). All used and unused study drug dispensed to subjects must be returned to the site.

Study drug accountability records will be provided to each study site to:

- Record the date received and quantity of study drug
- Record the date, subject number, subject initials, the study drug blister card number/bottle number dispensed
- Record the date, quantity of used and unused study drug returned, along with the initials of the person recording the information

Institution-specific accountability records may be used if they capture the same information listed above.

5.5.1. Investigational Medicinal Product Return or Disposal

Gilead recommends that used and unused study drug supplies be destroyed at the site. If the site has an appropriate standard operating procedure (SOP) for drug destruction as determined by Gilead, the site may destroy used (empty or partially empty) and unused study drug supplies in accordance with that site's approved SOP. A copy of the site's approved SOP will be obtained for the electronic trial master file. If study drug is destroyed at the site, the investigator must maintain accurate records for all study drugs destroyed. Records must show the identification and quantity of each unit destroyed, the method of destruction, and the person who disposed of the study drug. Upon study completion, copies of the study drug accountability records must be filed at the site. Another copy will be returned to Gilead.

If the site does not have an appropriate SOP for drug destruction, used and unused study drug supplies are to be sent to the designated disposal facility for destruction. The study monitor will provide instructions for return.

The study monitor will review study drug supplies and associated records at periodic intervals.

For both disposal options listed above, the study monitor must first perform drug accountability during an on-site monitoring visit.

6. STUDY PROCEDURES

The study procedures to be conducted for each subject enrolled in the study are presented in tabular form in [Appendix 2](#) and described in the text that follows.

For subjects who discontinue idelalisib prior to IRC documented disease progression, every attempt should be made to keep the subject in the study and continue to perform regular assessments per the schedule of procedures (with the exception of PK sampling and CMV monitoring) until the subject meets criteria for study discontinuation (see Section [3.5.2](#)).

The investigator must document any deviation from protocol procedures and notify the sponsor or contract research organization (CRO).

Safety and tolerability assessments will include regular monitoring of AEs, changes from baseline in laboratory variables, physical examinations (PEs), vital signs, and special safety assessment like ECGs.

From the time of obtaining informed consent through the first administration of investigational medicinal product, record all SAEs, as well as any non-serious AEs related to protocol-mandated procedures on the AEs eCRF. All other untoward medical occurrences observed during the screening period, including exacerbation or changes in medical history are to be captured on the medical history eCRF. See Section [7](#) for additional details.

6.1. Study Procedure Descriptions

During the treatment period, all visits may be performed within the specified visit window as noted in the schedule of events (see [Appendix 2](#)).

6.1.1. Informed Consent

All subjects must sign and date the most recent IRB/IEC-approved informed consent form before any study procedures are performed.

6.1.2. Medical and Medication History

A complete medical and surgical history will be obtained during screening including disease history and prior therapies.

A history of all medication taken within the 3 months prior to screening and during the screening period will be obtained.

6.1.3. Physical Examination

A physical exam will be performed at screening and will include assessment of clinical signs and symptoms. The exam will be performed by a physician, a physician's assistant, or nurse practitioner qualified to perform assessments. Breast, genital, and rectal examinations are not required, unless warranted in the opinion of the healthcare provider.

A limited physical exam (consistent with standard institutional guidelines) should be performed at the following visits:

Subjects enrolled as of Protocol Amendment 5:

Weeks 12, 24, 36, 48, 60, and every 24 weeks thereafter.

Subjects enrolled prior to Protocol Amendment 5:

Weeks 8, 16, 24, 36, 48, 60, and every 24 weeks thereafter.

6.1.4. Vital Signs

At Screening, vital signs including oxygen saturation, systolic and diastolic blood pressure, heart rate, respiratory rate, temperature, and anthropometric measurements of height and weight will be measured by the investigator or qualified designee as per standard institutional guidelines.

6.1.5. Laboratory Assessments

Analytes to be tested are listed in [Table 6-1](#). Specific instructions for processing, labeling, and shipping samples will be provided in a Central Laboratory Manual.

Blood samples for hematology and chemistry will be collected at each study visit. Additional clinic visits may be needed to monitor absolute neutrophil count (ANC) at Weeks 14, 18, and 22.

At screening, blood samples will also be obtained for serum pregnancy (if applicable), HBV, HCV, and HIV.

Blood samples for coagulation will be collected at screening, baseline, Weeks 8, 16, 32, 48, every 12 weeks thereafter.

Blood samples for Beta-2 microglobulin will be collected at screening, Weeks 24, 48, every 12 weeks thereafter, and at the End of Treatment (EOT) visit.

Blood samples for CMV will be collected at screening, Weeks 4, 8, 12, 16, 20, 24, and every 4 weeks thereafter throughout the course of study drug treatment, (including during drug interruptions due to toxicity or AEs), and at the EOT visit.

Blood sample for CMV serology (immunoglobulin [Ig]G, IgM) will be collected at baseline (Day 1) only.

Blood samples for immune-monitoring will be collected at Screening, Weeks 4, 12, 24, every 12 weeks thereafter, and at the EOT and EOS visits. Immune-monitoring samples include:

- Lymphocyte subset panel using flow cytometry (immunophenotyping)
- Quantitative immunoglobulins: IgG, IgM, IgA, IgE
- Serum CH50 level

At any time during the study, abnormal laboratory parameters that are clinically relevant (eg, lead to clinical symptoms or signs, require therapeutic intervention), and constitute an AE must be recorded in the eCRF.

A urine sample for urinalysis will be collected at screening only.

Table 6-1. Analytes

Chemistry	Hematology	Urinalysis	Other
Albumin	ANC	pH	Serum β -hCG or urine for pregnancy test HIV antibody Hepatitis B surface antigen Hepatitis B core antibody Hepatitis C antibody Hepatitis C viral RNA CMV PCR Anti-CMV IgG and IgM Immunophenotyping Serum CH50 level
Alkaline phosphatase	RBC	Protein	
ALT/SGPT	Hemoglobin	Glucose	
AST/SGOT	Hematocrit	Ketones	
Bicarbonate	Platelets	Bilirubin	
Calcium	WBC	Urobilinogen	
Chloride		Blood	
Cholesterol	Differential	Nitrite	
Creatinine ^b	Neutrophils	Leukocyte esterase	
GGT	Eosinophils		
Glucose	Basophils		
LDH	Lymphocytes		
Phosphorus	Monocytes		
Potassium	Bands		
Sodium			
Total bilirubin ^a	Coagulation	Quantitative Immunoglobulins	
Total protein	PT/INR	IgA	
Triglycerides	aPTT/PTT	IgE	
Uric acid		IgG	
BUN		IgM	

a Includes direct bilirubin

b Estimated glomerular filtration rate will be calculated according to the Cockcroft-Gault formula for creatinine clearance. Creatinine clearance is only measured at screening.

6.1.5.1. Pregnancy Test

All females of childbearing potential (see [Appendix 4](#)) will have a serum pregnancy test at screening. Urine pregnancy tests will be performed at baseline, and every 4 weeks thereafter. The pregnancy testing is more frequent than regular clinic visits after Week 24. Urine pregnancy tests will also be performed at the EOT and EOS visits.

6.1.5.2. Pharmacokinetics

Blood samples will be collected for PK assessments at baseline, Weeks 2, 4, 6, 8, 10, 12, 16, 20, 24, 32, and 48 predose (within 1 hour prior to dose) and 1.5 hours (\pm 10 min) post dose in the morning. If prior scheduled dose was missed for any reason including due to planned “off-treatment” schedule, a predose PK sample is not needed. A single non-timed PK sample will also be collected at any unscheduled study visit through Week 48.

For subjects randomized to Arm C, study drug should not be taken on scheduled “off-treatment” days, regardless of prior missed doses, study drug interruptions for toxicity, or PK samples.

6.1.5.3. CCI [REDACTED]

CCI [REDACTED]

6.1.5.4. CCI [REDACTED]

6.1.5.5. Evaluation for Gastrointestinal Events/Colitis

For Grade 2 colitis and diarrhea (unless clinical diagnosis is established from medical history and physical examination), the following testing is required:

- Stool culture for routine pathogens (*Salmonella*, *Shigella*, *Campylobacter* species, *Clostridium difficile* toxin, Rotavirus, Cytomegalovirus, Adenovirus)
- Stool for Ova and Parasites (*Cryptosporidium parvum*, *Isospora belli*, *Enterocytozoon bieneusi*, *Septata intestinalis*, *Strongyloides*, *Microsporidia*, *Entamoeba histolytica*, *Cyclospora*), *Giardia* antigen

For Grade \geq 3 or persistent Grade 2 colitis or diarrhea without clear etiology (eg, *clostridium difficile* enterocolitis), endoscopy with biopsy is recommended. All biopsy samples should include immunohistochemistry and polymerase chain reaction (PCR) for CMV and adenovirus.

CCI [REDACTED]

See Section 6.1.12.1 for additional requirements (ie, collection of information and physical exam) when an AE of diarrhea or colitis occurs.

6.1.5.6. Differentiation Between Small-Bowel and Large-Bowel Diarrhea

Differentiation between small-bowel and large-bowel diarrhea: may be possible on a clinical basis. If unclear, consider upper and lower tract endoscopy with biopsy.

- Small bowel diarrhea is characterized by large volume diarrhea (more than one per day), possibly associated dehydration weight loss and paraumbilical pain. Consider an endoscopic small-bowel biopsy and evaluate other etiologies such as celiac disease.
- Large-bowel diarrhea may present with lower pelvic pain, tenesmus, generally smaller stool volume with gross blood frequently found in the stool. Consider a colonoscopic evaluation and biopsy.

6.1.6. Electrocardiogram Assessment

A standard 12-lead ECG will be performed at screening as per standard institutional practice.

6.1.7. Radiology Assessment

Subjects will be imaged at neck, chest, abdomen, and pelvis with either PET-CT (diagnostic), contrast-enhanced CT, or gadolinium-enhanced MRI. If MRI is chosen, subjects will have an MRI of neck, abdomen, and pelvis, but will need a non-contrast enhanced CT of the chest. Chest x-ray, ultrasound, endoscopy, laparoscopy, radionuclide scans, or tumor markers will not be considered for response assessment. For radiographic evaluations, the same method of assessment and the same technique (eg, scan type, scanner, subject position, dose of contrast, injection/scan interval) should be used to characterize each identified and reported lesion at baseline and during study participation.

All relevant clinical and radiographic information required to make each assessment must be made available for source verification and for submission to the IRC.

Investigators will assess the status of each subject's disease using standard response criteria.

If disease progression is suspected, the IRC will be notified and radiographic images will be submitted to the IRC.

The IRC will review radiographic and pertinent clinical data in order to provide a definitive interpretation. The findings of the IRC will be considered primary for analyses of efficacy endpoints. It is recommended that the investigator consults with the medical monitor if considering removing a subject from study prior to a definitive IRC assessment of progression.

Radiographic assessments will be performed at the following visits:

Subjects enrolled as of Protocol Amendments 5 and 6:

Screening, Weeks 12, 24, 36, 48, 60, and 84 until IRC documented disease progression, and at EOT (unless radiographic assessments performed within 4 weeks prior to EOT visit). After Week 84, radiographic assessments are performed at the discretion of the investigator. Screening CT/PET-CT/MRI may be performed within 6 weeks prior to first dose. Subsequent scans may be done within 1 week prior to clinic visit.

Subjects enrolled prior to Protocol Amendment 5:

Screening, Weeks 8, 16, 24, 36, 48, 60, and 84 until IRC documented disease progression, and at EOT (unless radiographic assessments performed within 4 weeks prior to EOT visit). After Week 84, radiographic assessments are performed at the discretion of the investigator. Screening CT/PET-CT/MRI may be performed within 6 weeks prior to first dose. Subsequent scans may be done within 1 week prior to clinic visit.

6.1.8. Bone Marrow Biopsy

For subjects in whom a radiologic CR is determined, a bone marrow biopsy may be required for complete assessment. In a subject who has a baseline or on-study bone marrow biopsy showing involvement with lymphoma or does not have a baseline bone marrow examination, declaration of an on-study CR requires bone marrow biopsy documentation of the absence of lymphoma. In a subject who has a baseline or on-study bone marrow biopsy showing no evidence of lymphoma, declaration of an on-study CR does not require bone marrow examination as long as other criteria for CR are met.

6.1.9. Performance Status

Performance status may be scored using the ECOG or Karnofsky Performance Status Scoring Systems at screening, Weeks 8, 16, 32, 48, every 12 weeks thereafter, and at the EOT and EOS visits.

6.1.10. Baseline Prognostic Factors, Ann Arbor Stage and FLIPI

At Screening, prognostic factors will be assessed. All subjects will have Ann Arbor stage assessments recorded ([Appendix 3](#)) and FLIPI factors assessed and scores calculated. FLIPI scores are a composite of 5 factors: age, number of nodal sites, Ann Arbor stage, hemoglobin level, and LDH level ([Appendix 5](#)).

6.1.11. Study Drug Dispensing and Dosing

Study drug will be dispensed at Baseline (Day 1), Weeks 4, 8, 12, 16, 20, 24, 32, 40, 48, and every 12 weeks thereafter until EOT. Drug may also be dispensed at unscheduled visits if necessary. Idelalisib will be administered as per Section [5.3](#).

6.1.12. Adverse Events

Adverse events will be assessed at all study visits. From the time of obtaining informed consent through the first administration of study drug, record all SAEs as well as any non-serious AEs related to protocol-mandated procedures on the AE eCRF. All other untoward medical occurrences observed during the screening period, including exacerbation or changes in medical history are to be captured on the medical history eCRF.

From the time of obtaining informed consent through 30 days post the last administration of study drug, record any AEs related to protocol-mandated procedures or study drug on the AE eCRF. SAEs should be captured on the SAE eCRF.

See Section 7 (Adverse Events and Toxicity Management) for additional details.

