7.1.2. Serious Adverse Events

An SAE is defined as an event that, at any dose, results in the following:

- Death
- A life-threatening situation (Note: The term “life-threatening” in the definition of “serious” refers to an event in which the subject was at risk of death at the time of the event; it does not refer to an event that hypothetically might have caused death if it were more severe.)

- In-patient hospitalization or prolongation of existing hospitalization
- Persistent or significant disability/incapacity
- A congenital anomaly/birth defect
- A medically important event or reaction: such events may not be immediately life-threatening or result in death or hospitalization but may jeopardize the subject or may require intervention to prevent one of the other outcomes constituting SAEs. Medical and scientific judgment must be exercised to determine whether such an event is a reportable under expedited reporting rules. Examples of medically important events include intensive treatment in an emergency room or at home for allergic bronchospasm; blood dyscrasias or convulsions that do not result in hospitalization; and development of drug dependency or drug abuse. For the avoidance of doubt, infections resulting from contaminated medicinal product will be considered a medically important event and subject to expedited reporting requirements

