7.2.2. Assessment of Severity

The severity of AEs will be graded using the CTCAE, Version 5.0. For each episode, all increases in severity/grade should be reported.

If a CTCAE criterion does not exist, the investigator should use the grade or adjectives: Grade 1 (mild), Grade 2 (moderate), Grade 3 (severe), Grade 4 (life-threatening), or Grade 5 (fatal) to describe the maximum intensity of the AE. For purposes of consistency with the CTCAE, these intensity grades are defined in [Table 7-1](#).

Table 7-1. Grading of Adverse Event Severity

Grade	Adjective	Description
Grade 1	Mild	Sign or symptom is present, but it is easily tolerated, is not expected to have a clinically significant effect on the subject's overall health and well-being, does not interfere with the subject's usual function, and is not likely to require medical attention.
Grade 2	Moderate	Sign or symptom causes interference with usual activity or affect clinical status, and may require medical intervention.
Grade 3	Severe	Sign or symptom is incapacitating or significantly affects clinical status and likely requires medical intervention and/or close follow-up.
Grade 4	Life-threatening	Sign or symptom results in a potential threat to life.
Grade 5	Fatal	Sign or symptom results in death.

The distinction between the seriousness and the severity of an AE should be noted. Severe is a measure of intensity; thus, a severe reaction is not necessarily a serious reaction. For example, a headache may be severe in intensity, but would not be classified as serious unless it met one of the criteria for serious events listed in Section 7.1.2.

7.3. Investigator Requirements and Instructions for Reporting Adverse Events and Serious Adverse Events to Gilead

All SAEs, regardless of cause or relationship, that occur after the subject first consents to participate in the study (ie, signing the informed consent) and throughout the duration of the study, including the protocol-required posttreatment follow-up period, must be reported in the eCRF database and Gilead PVE as instructed. This also includes any SAEs resulting from protocol-associated procedures performed from Screening onwards.

All AEs, regardless of cause or relationship, which occur from initiation of study drug until 30 days after last administration of study drug must be reported to the eCRF database as instructed.

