8.6.2. Adverse Events

All AEs will be listed. The focus of AE summarization will be on treatment-emergent AEs. A treatment-emergent AE is defined as any AE with onset date on or after the date of first dose of study drug up to 30 days after permanent study drug discontinuation or any AEs leading to premature study drug discontinuation.

AEs will be classified using Medical Dictionary for Regulatory Activities with descriptions by system organ class (SOC), high-level group term, high-level term, preferred term (PT), and lower-level term. The severity of AEs will be graded by the investigator according to the CTCAE, Version 5.0, whenever possible. If a CTCAE criterion does not exist for a specific type of AE, the grade corresponding to the appropriate adjective will be used by the investigator to describe the intensity of the AE: Grade 1 (mild), Grade 2 (moderate), Grade 3 (severe), Grade 4 (life threatening), or Grade 5 (fatal). The relationship of the AE to the study drug will be categorized as related or unrelated.

For the primary safety endpoint, the number and percentage of subjects who experienced at least one Grade ≥ 4 TEAE will be listed and summarized by SOC and PT, and by treatment arm in the Safety Analysis Set. The severity, timing, relationship to study drug, drug interruptions, reductions, and discontinuations for Grade ≥ 4 TEAEs will be summarized.

Summaries (number and percentage of subjects) of TEAEs by SOC and PT will be provided. A subject who reports multiple TEAEs within the same PT (or SOC) is counted only once for that PT (or SOC) using the worst severity grade. AE descriptions will be presented by decreasing frequency for a given SOC and PT.

Separate summaries will be prepared for the following types of TEAEs:

- Idelalisib-related AEs
- AEs that are Grade ≥ 4 in severity

- AEs that are Grade ≥ 3 in severity
- AEs leading to study drug interruption, reduction, or discontinuation
- SAEs

Additional analysis on AEs will be performed. The AEs include: Grade ≥ 3 diarrhea/colitis, rash, febrile neutropenia, infection, and any grade of the following: pneumonitis, bowel perforation, progressive multifocal leukoencephalopathy (PML), PJP, CMV infection, and organizing pneumonia. The frequency, severity, timing, and drug interruptions for AEs will be summarized by treatment arm using descriptive statistics. Time to first onset of AEs and time to resolution will be summarized using the Kaplan-Meier method.

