7.1.5. Treatment-Emergent Adverse Events

7.1.5.1. Definition of Treatment-Emergent Adverse Events

Treatment-emergent adverse events (TEAEs) are defined as 1 or both of the following:

- Any AEs with an onset date on or after the study drug start date and no later than 30 days after permanent discontinuation of study drug
- Any AEs leading to permanent discontinuation of study drug.

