7.1.6.1. Summaries of Adverse Events Incidence by Severity

The number and percentage of subjects who experienced at least 1 TEAE will be provided and summarized by SOC and PT.

The number and percentage of subjects who experienced at least 1 TEAE will be provided and summarized by PT and severity in descending order of total frequency:

- Treatment-Emergent Adverse Events by PT and Severity

For the AE categories described below, summaries will be provided by PT in descending order of total frequency:

- All Treatment-Emergent Adverse Events
- Grade 4 or Higher Treatment-Emergent Adverse Events
- Grade 3 or Higher Treatment-Emergent Adverse Events
- Treatment-Emergent Idelalisib related Adverse Events
- Treatment-Emergent Serious Adverse Events
- Treatment-Emergent Idelalisib related Serious Adverse Events
- Treatment-Emergent Adverse Events leading to discontinuation of Idelalisib
- Treatment-Emergent Adverse Events leading to temporary interruption of Idelalisib
- Treatment-Emergent Adverse Events leading to study discontinuation
- Treatment-Emergent Adverse Events leading to Death

A brief, high-level summary of AEs described above will be provided by treatment arms and by the number and percentage of subjects who experienced the above AEs.

For summaries of TEAEs by PT, multiple events will be counted only once per subject in each summary. Adverse events will be summarized and listed by PT in descending order of total frequency. For summaries by severity, the most severe severity will be used for those AEs that occurred more than once in a given subject during the study.

In addition, by-subject data listings will be provided by treatment arms and subject ID number in ascending order for the following:

- All AEs, indicating whether the event is treatment emergent
- All SAEs
- All Deaths
- All Adverse Events leading to Death
- All Adverse Events with Grade 3 or Higher
- All Adverse Events with Grade 4 or Higher

- All Adverse Events leading to discontinuation of Idelalisib
- All Adverse Events leading to temporary interruption of Idelalisib
- All Adverse Events leading to study discontinuation

A flag will be included in the listings to indicate whether the event is treatment emergent.

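### The AE recording rule in Protocol 6.1.12 is narrower than 7.3 and the all-cause TEAE analyses; separately, the CD4+ threshold for stopping PJP prophylaxis is printed in two units

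*Protocol*

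**What the plan says.** **AE recording.** Protocol 6.1.12 has two rules. Before the first dose, sites record SAEs and procedure-related non-serious AEs. From consent to 30 days after the last dose, they are to "record any AEs related to protocol-mandated procedures or study drug on the AE eCRF", with SAEs on their own form. The section closes by referring to Section 7 for more detail.

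Protocol 7.3 requires reporting to the eCRF database of "All AEs, regardless of cause or relationship, which occur from initiation of study drug until 30 days after last administration of study drug". It also requires all SAEs from consent, whatever the cause.

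The analyses follow the wider rule. Protocol 8.6.2 defines a TEAE as "any AE with onset date on or after the date of first dose of study drug up to 30 days" after permanent discontinuation. SAP 7.1.5.1 has "Any AEs with an onset date on or after the study drug start date and no later than 30 days" after that point. Both also count AEs that lead to discontinuation, and neither limits TEAEs by relatedness. SAP 7.1.6.1 tabulates "Grade 4 or Higher Treatment-Emergent Adverse Events" and Grade 3 or higher TEAEs separately from idelalisib-related TEAEs.

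**CD4+ threshold.** Protocol 7.5.6 allows PJP prophylaxis to stop, between 2 and 6 months after idelalisib ends, once the CD4+ count exceeds 200 cells/mL. Appendix 2 footnote o cites 7.5.6 for the same rule but gives 200 cells/mcL. Footnote p sends sites back to 7.5.6 for when prophylaxis may end.

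**The concern.** Section 6.1.12 is the procedures text for AE recording. A site that works from it alone would enter related AEs and SAEs, and could leave out a non-serious AE that the investigator judges unrelated. Such an event is still a TEAE under both documents. The all-cause summaries would then describe something between all-cause and related events, and the mix would vary by site.

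Relatedness is an investigator judgement (Protocol 7.2.1), and from Amendment 5 the study is open-label. Protocol 1.3 asks whether Arm C gives similar efficacy with less toxicity. A filter that depends on relatedness could therefore act differently in Arms A and C. The direction cannot be told from the documents. The SAP plans no formal tests (3.5), so the effect would be on the descriptive comparison.

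The CD4+ figure is a stopping threshold for infection prophylaxis in patients at risk of PJP. If it is read literally in cells/mL, it screens out almost nobody.

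**Working it through.** No sample-size, power or alpha figure is in dispute. The check on AE recording traces each kind of AE to the text that would cause it to be entered.

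1. **SAEs, any grade.** Protocol 7.3 requires them regardless of cause, and 6.1.12 sends them to the SAE form with no relatedness limit. Nothing is lost.
2. **Non-laboratory Grade 4 events.** Table 7-1 describes Grade 4 as "Sign or symptom results in a potential threat to life". That largely coincides with the life-threatening criterion for an SAE in 7.1.2, so these mostly fall under item 1.
3. **Laboratory Grade 4 events.**
   - Clinically relevant abnormalities that meet the conditions in 6.1.5 "and constitute an AE must be recorded in the eCRF", with no causality filter.
   - Section 7.1.3 requires entry of abnormalities that need intervention or lead to dose interruption, modification or discontinuation. Table 5-2 requires a hold or a stop for Grade 4 ALT/AST, bilirubin, neutropenia and thrombocytopenia.
   - Section 7.1.2 names "blood dyscrasias or convulsions that do not result in hospitalization" among its examples of medically important events.
   - Abnormalities without clinical significance are not recorded as AEs under 7.1.3. That holds under 7.3 as well, so the conflict loses nothing here.
   - A thin remainder is possible. Section 5.3.2 expects exceptions to dose rules for subjects who start with low counts, and after permanent discontinuation no dose action can trigger entry. The 6.1.5 rule and the SAE criteria still apply to these.
4. **Non-serious, non-laboratory AEs judged unrelated.** Only 7.3 clearly brings these in. Most will be Grade 1 to 3. Protocol 7.2.2 itself notes that a severe headache need not be serious, so some Grade 3 events belong here. This is where the two rules part.

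**Scale for the primary endpoint.** Let r be the true share of subjects with a Grade ≥ 4 TEAE. Let u be the fraction of those subjects whose only such events were non-serious, judged unrelated and not entered. The recorded share is r × (1 − u). Protocol 1.3 gives r = 23/72 = 32% in Study 101-09. The documents give no value for u, so the range below is an assumption.

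- u = 0: 32%.
- u = 10%: 0.32 × 0.90 = 28.8%.

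The lower figure needs one in ten affected subjects to have had no serious, related or otherwise recordable Grade ≥ 4 event. Items 1 to 3 make that unlikely. No comparable scale can be given for item 4, because the documents report no rate of unrelated, non-serious AEs.

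**CD4+ unit.** 1 mL = 1000 mcL, so 200 cells/mL = 200 / 1000 = 0.2 cells/mcL. The ratio of the two thresholds is 200 / 0.2 = 1000.

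**The case against.** Section 6.1.12 does not say that only related AEs are recorded, and it sends the reader to Section 7. Section 7.3 is headed as the investigator's reporting requirements and uses mandatory language. A site that follows 7.3 satisfies both texts. The rest of the plan presumes that unrelated AEs are collected: the AE definition in 7.1.1 is all-cause, 7.2.1 provides a No answer for causality, 9.1.5 expects source records of all AEs, 8.6.2 classes AEs as related or unrelated, and SAP 7.1.3 shows that the AE form asks about relatedness. The eCRF completion guidelines, which we do not have, may settle the matter, and 9.1.6 and 9.3.2 provide for data review and monitoring.

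Most of this stands, and it makes systematic loss unlikely. It does not remove the conflict. The reference to Section 7 is for further detail and sets no order of precedence, and the two sections state different rules for the same window.

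On the CD4+ unit, a micro sign may have been lost when the PDF was read. Micro signs survive in the eligibility table and Appendix 7, but that does not show how the body text was read. Footnote o already carries the plausible unit. Even read literally, 7.5.6 keeps a 2-month minimum, advises 2 to 6 months and leaves longer duration to clinical judgement. This point therefore stays conditional on the source PDF.

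**Conclusion.** The recording rule in 6.1.12 is too narrow as written and should be aligned with 7.3. The exposure is under-recording of non-serious AEs judged unrelated, in the all-cause TEAE and Grade ≥ 3 summaries, at sites that follow 6.1.12 alone. Its size is unknown.

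A reader might infer that the Grade ≥ 4 primary endpoint is materially under-collected. The documents do not support that. Nearly all such events are caught regardless of causality by SAE reporting, the laboratory rules in 6.1.5 and 7.1.3, or the dose actions in Table 5-2. Grade 4 laboratory values without clinical significance are outside AE recording under either rule. The effect on that endpoint is probably very small. This rests on sites applying the seriousness and laboratory rules as written.

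The CD4+ discrepancy is 1000-fold in the text available and concerns a safety threshold. Whether it is an error in the protocol depends on the unit printed in the source PDF.

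**What to change.** Replace the second recording rule in 6.1.12 with the scope of 7.3: all AEs, whatever their cause or relationship, from the first dose to 30 days after the last dose. Keep procedure-related AEs and all SAEs from consent. This is a change of one sentence and adds nothing to what 7.3 already requires.

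Check 7.5.6 in the source PDF. If it prints mL, change the unit to cells/mcL to match Appendix 2 footnote o. This is a one-word correction.

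A listing of Grade 4 laboratory values with no matching AE is not needed for this point. It would test how sites applied 7.1.3, which is a different question.

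SAP Section 1 says the study was terminated early. If no subject remains within the 30-day window or on prophylaxis, the wording changes can no longer affect collection or care. A sentence in the clinical study report on which AE rule sites were given would then be enough.
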